24. LOCAL RECRUITMENT METHODS

Patient participant recruitment will be similar in all phases of the study in which Research Assistants (RAs) will review the electronic health record dashboard and document all patients who present during their shift on a Screening Log. Additionally, they will use medical records and consultation with clinical staff to determine if an individual is appropriate to approach.

The RA will approach each patient in his/her room after the patient has been medically assessed and stabilized by medical staff. The RA will explain the nature, purpose, risks, and benefits of the study. If eligible and the patient is interested in participating, the consent process will be conducted in-person; the research staff will verbally review the consent and HIPAA forms with the participant in REDCap. We will let the participant review an electronic copy of the consent upon request. The participant and the research staff will both electronically sign through REDCap's "Signature" feature. The participant will then choose whether they would like to receive an emailed PDF copy of the consent or a PDF paper copy of the consent sent to their address. Depending on which they choose, the REDCap survey will then branch to either enter the participant's email address or mailing address. The subject's email/home address will be deleted as soon as the consent form has been sent to the subject and are not being collected as part of the study design. See grant: "HUMAN PARTICIPANTS PROTECTION" (p.19) "Informed Consent" for additional details.

For the clinician participant not associated with a patient participant, recruitment will occur via email to providers in the ED, inpatient units, and outpatient units who are X-waivered to prescribe MAT to UMass patients with OUD. The RA will send an email to these providers with the User Testing Fact Sheet and Aims of the project attached with a request to respond to the email if they are interested in learning more and potentially participating in the study. For those

who respond with interest, the RA will set up a time to meet in person in a private office to review the User Testing Fact Sheet and ask questions. After reviewing the User Testing Fact Sheet, if clinicians are interested in participating, they will verbally consent to participate.

For clinicians at the UMass Bridging Clinic, at the CleanSlate Addiction Treatment Center, at SaVida Health, at Spectrum Health Systems, Eleanor Health, and Right Choice who will be working with patient participants referred to the clinic, the RA will send an email to these providers with the Dyad Fact Sheet and Aims of the project attached with a request to respond to the email if they are interested in learning more and potentially participating in the study. For those who respond with interest, the RA will set up a time to meet in person to review the Dyad Fact Sheet and ask questions. After reviewing the Dyad Fact Sheet, if clinicians are interested in participating, they will verbally consent to participate.

Phase 1 Aim 1 (Develop OARSCM): After the RA consents the patient participant, the RA will help the participant download the OARSCM mobile application on either their personal smartphone or study-provided iPad. The participant will then enter their name (first and last), DOB, email, and cell phone number when available into the OARSCM mobile application for registration. The RA will then instruct the participant on how to use the OARSCM mobile application and guide them through tasks on the application such as reviewing their scheduled appointments, journaling and using prize draws. The RA will then interview the participants on the usability of the OARSCM mobile application. After the usability survey, the RA will also instruct the participant on how to delete the OARSCM mobile application should they no longer want the mobile application on their phone at the end of the study. If participants do not have their personal smartphone available at the time of enrollment, they will be given a handout with instructions for how to download and delete the OARSCM mobile application. Patient participant will then receive standard clinical care for their substance use, including gathering a recent history of their substance use using the timeline followback and addiction severity index to assist in the referral, connecting them to the UMass Bridge Clinic, CleanSlate Addiction Treatment Center, SaVida Health, or Spectrum Health Systems treatment provider, and scheduling an intake appointment at the Bridge Clinic, at CleanSlate, at SaVida Health, or at Spectrum Health Systems. At the end of the study period, participant OASRCM account access will be removed.

In Phase 1, all patient participants who complete the intake process and usability interview will receive \$30 remuneration for enrollment during their hospital visit. In addition to the \$30 they receive during their hospital visit, they are eligible for additional prizes earned in the OARSCM mobile application for engagement in MAT treatment. Prizes come in the form of electronic gift cards in the mobile application to Amazon, Dunkin' Donuts and Walmart and are available of increments of \$5, \$20, and \$100. Patients are able to earn \$1 prizes which they will need to save until they reach \$5 to claim a gift card. Patient participants do not receive follow-up calls. See grant: "RESEARCH STRATEGY" (p. 3) for complete schedule of prize potential and earnings.

For the clinician participant not associated with the UMass Bridge Clinic, with the CleanSlate Addiction Treatment Center, with SaVida Health, or with Spectrum Health Systems who responded to the email with interest in potentially participating, the RA will schedule a time for the clinician participant to learn more and conduct the interview. Providers will be instructed to

access OARSCM through either a work computer or a work tablet PC, with the standard UMMHC security capabilities that are in place throughout the system, as well as the Q2i security features that are in place for the patients, such as, all confidential data is stored encrypted and is only stored in authenticated services. Prior to conducting the interview, all clinicians will be given the User Testing Fact Sheet in person and the opportunity to ask questions about the study. For those who review the User Testing Fact Sheet and verbally agree to participate, they will be given a clinician study ID that will be recorded at the top of User Testing Fact Sheet and a copy will be given to the clinician. The RA will then instruct the clinician to create a test account in the provider portal and guide them through user tasks in the portal. The RA will then interview the participants on the usability of the provider portal. The clinicians participating in usability testing will not receive remuneration for their participation.

For the clinician participant associated with the UMass Bridge Clinic, with the CleanSlate Addiction Treatment Center, with SaVida Health, or with Spectrum Health Systems (dyad) who responded to the email with interest in potentially participating, the RA will schedule a time for the clinician participant to learn more and complete a training on how to use the OARSCM provider portal to track patient participant progress in treatment. Providers will be instructed to access OARSCM through either a work computer or a work tablet PC, with the standard UMMHC security capabilities that are in place throughout the system, as well as the Q2i security features that are in place for the patients, such as, all confidential data is stored encrypted and is only stored in authenticated services. Prior to completing the training, all clinicians will be given the Dyad Fact Sheet in person and the opportunity to ask questions about the study. For those who review the Dyad Fact Sheet and verbally agree to participate, they will be given a clinician study ID that will be recorded at the top of the Dyad Fact Sheet and a copy will be given to them. The RA will then train the clinician on how to create an OARSCM provider account using their name (first and last) and email address and walk them through how to use the OARACM provider portal to track patient participant treatment progress. After the clinician has completed treatment with at least one patient participant, the RA will reach out the clinician to schedule a time to conduct the interview on the usability of the provider portal. Once the patient has completed their 4 weeks in the study, they will become archived on the provider portal, and the provider will not be able to see that particular patient's information. The provider's general portal will be active for longer than 4 weeks as they will have more than one patient who will be completing the study at different times. In phase 1, the clinical information that the provider enters (appointment attendance and tox results) are accessible to the provider through the EHR (EPIC). The clinicians participating in the dyad portion of the study will not receive remuneration for their participation.

Phase 2 Aims 1 & 2 (RCT of OARSCM): Patients will complete a screening survey to assess for minimal eligibility criteria and confirm their interest. If a potential participant is deemed ineligible for the study, they will be informed that they are not a good fit for this study and the screening form will be shredded immediately after the encounter. After the RA consents the participant, they will open a randomization envelope and randomize the patient to either TAU or OARSCM. For TAU the participant will receive SBIRT provided by the RA, a warm handoff to a community MOUD treatment facility and will be trained on how to use MyMAT (an educational mobile application). For OARSCM the participant will receive TAU as described

above with the addition of the OARSCM mobile application instead of MyMAT. Participants will be trained on how to use the OARSCM mobile application, potentially earning prizes throughout treatment as part of contingency management. After leaving the ED, participants will complete follow-up calls at 1, 3, and 6-month time periods.

In Phase 2, all participants will receive an initial \$25 remuneration for enrollment during their ED visit, an additional \$30 per follow-up call (1 and 3 months), and an additional \$35 for completing the 6-month follow-up call for a total of \$120/participant. Those randomized to the contingency management group have to opportunity to earn additional money as part of treatment. See grant: "RESEARCH STRATEGY" (p12) "Procedures" for further details.

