5. BACKGROUND*

See grant: "RESEARCH STRATEGY" (p.2-4) for details. The Procedures for Phase 2 have been modified from the original submission. Updated Procedures are as follows:

Procedures

Screening, recruitment, eligibility and training procedures are in C.2.1 and the Eligibility criteria document.

Randomization will occur following determination of eligibility using an urn procedure and stratifying on 1) other (than opioid) substance use disorder no/yes, 2) gender/sex, 3) race/ethnicity.

TAU with MyMAT (n = 51). In the acute care setting, the Behavioral Health Service run by Drs. [name] and [name] provides SBIRT for substance use disorders, including OUD. They provide SBIRT as part of TAU, including, when possible, warm handoff contact with outpatient MOUD treatment that includes a scheduled outpatient appointment, optimally within 48 hours of the ED visit. Patients randomized to this group will also receive MyMAT, a mobile application with opioid treatment educational content, as an attention control measure against OARS+CM. TAU outpatient suboxone treatment consists of urine toxicology screening, group/individual therapy, and MOUD prescription continent on drugnegative (except cannabis, which is legal in MA) urine toxicology. Treatment visits are typically, weekly in weeks 1-4 and then taper over time, to every other week in weeks 5-8, and monthly in weeks 9-12 and thereafter. Nonadherence can lead to increased frequency/intensity of therapy and urine toxicology until the patient stabilizes. If increased frequency/intensity is unsuccessful, patients may be referred to detoxification and subsequently re-admitted to outpatient care when appropriate.

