Group A: TAU with MyMAT. For TAU participants, the usual care provided to individuals with OUD at the UMass University and Memorial hospitals will be provided. This typically consists of (1) medical stabilization and treatment, as needed; (2) brief counseling and referral to treatment by a social worker or other behavioral health provider, which includes providing a tailored referral list; and (3) when the patient is interested and treatment facility available, a "warm handoff" comprised of contact with the outpatient provider and transportation directly to the facility or a scheduled intake appointment within 48 hours, when feasible. TAU participants will also receive MyMAT, a mobile application with opioid treatment educational content, as an attention control measure against OARS+CM.

Group B: OARS+CM. Participants assigned to OARS+CM will receive the same treatment as in the TAU condition but with the enhancement of the CM features, described in detail in Section C.2.1, Proof-of-concept testing for usability section.

Table 1: Eligibility criteria						
Inclusion	Exclusion					
→ >= 18 years old	 Persistent altered mental status (not alert, not oriented, psychotic). 					
◆ Presenting for acute care at UMass University and Memorial hospitals, including EDs, inpatient medical units, inpatient behavioral health units, or community acute care partners for opioid addiction related health complaints, including opioid overdose, opioid related medical consequences, opioid intoxication or withdrawal syndromes, and/or seeking help for OUD	Patient declines referral to UMass Bridging MAT Clinic, to CleanSlate Addiction Treatment Center, to SaVida Health, to Eleanor Health, or to Spectrum Health Systems for MOUD.					
 Presence of a current DSM-V opioid use disorder (OUD), mild to severe 	 Not interested or willing to participate in MOUD treatment 					
 Medically appropriate for outpatient MOUD treatment, as judged by the 	 Unwilling to use the OARS+CM app (if assigned) 					
treating clinician and behavioral health consultant or toxicologist working with the patient clinically	 Does not have access to their own smartphone with at least iOS 7.1 or Android 4.2, the minimal technology required to run the app, or not willing to access clinic- dedicated computer to access the program 					

	Currently a UMMS student			
 Treatment provider of patient who 	 Prisoner or currently in state custody or 			

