11. PROCEDURES INVOLVED*

Measures: For Phase 1, the System Usability Scale (SUS) (patients and clinicians), Timeline Followback (TLFB) (patients only), and Addiction Severity Index (ASI) (patients only) will be used and is included in this submission. For Phase 2, The Mini Quiz (MQ), Mini-Usability Acceptability Testing (Mini-UAT) questionnaire, Timeline Followback (TLFB), PROMIS Pain Intensity and Interference Scales (PIIS), HIV Risk Behavioral Scale (HRBS), Post-traumatic Stress Diagnostic Scale for DSM-5 (PDS), Treatment Satisfaction Scale (TSS), and the System Usability Scale (SUS) will be used and are included in this submission.

Assessments/Procedures for Phase 2	Intake	Onboarding	Transition to Suboxone	Week 1 to 12	Month 1	Month 3 / End of Tx	Month 6
Mini Quiz, Patient form, OUD	X						
Mini-UAT, Service Utilization, TLFB	X				Х	Х	Х
PIIS, HRBS, PDS, U-Tox	X				Х	Х	Х
Healthcare Utilization	X						Х
App training, warm hand-off scheduling outpatient Suboxone intake		Х					
Monitor completion of MOUD intake			Х				
MOUD TAU / OARS+CM				Х			
Monitor treatment attendance/u-tox				X			
Treatment satisfaction, SUS*						Х	

^{*}Only for OAR+CM group

Phase 1: Aim 1 (Develop OARSCM): 30 Clinicians (20 user testing, 10 dyads) and 30 Patients

- 1a. After the OARSCM is developed, patients meeting criteria and consenting to participate will be guided through using the mobile application on their personal smartphone. If the participant's smartphone is not available for use to complete the instructed tasks, the participant will be able to use a study-provided iPad.
- 1b. Clinicians not associated with a specific patient participant verbally consenting to participate after reviewing the User Testing Fact Sheet will be guided through using the provider portal using a test account on a study provided computer in a private office.
- 1c. Clinicians working at the UMass Bridge Clinic, at the CleanSlate Addiction Treatment Center at SaVida Health, and at Spectrum Health Systems associated with a patient participant (considered a dyad) verbally consenting to participate after reviewing the Dyad Fact Sheet will receive an in-person or virtual training on the provider portal on a study provided computer in a private office. After the training, the clinician will provide standard MAT treatment to patient participants and use the OARSCM provider portal to track treatment.

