23. RESOURCES AVAILABLE

Research Personnel. Investigators and key personnel will have undergone mandatory education in human research participants' protection. Educational systems are in place to ensure that all research staff have been through such training and are approved by the IRB Human Subjects department. The responsibilities of investigators and research personnel are as follows:

Principal Investigator. The Principal Investigator will be responsible for overall project governance at UMass, leadership of the Project Team at UMass, protocol development, informing the data analytic plan, and dissemination efforts through professional presentations and peer reviewed journal publications

Co-Investigator. The Co-Investigators will be responsible for collaboration with other MOUD providers in the region and overseeing communication between research staff and community MOUD providers. Other responsibilities include overseeing contingency

management plan development and implementation and advising the team on data management and quality assurance protocols.

Project Manager. The Project Manager will be responsible for managing daily operations of recruitment and enrollment including training and supervising the research assistants. They will manage all IRB related submissions, amendments, and reporting.

Research Assistant(s). The research assistant(s) will be responsible for reviewing the electronic health record dashboard each shift and documenting potentially eligible patients on a Screening Log. They will be responsible for enrolling participants conducting interviews and completing telephone outcome assessment services for the stud(ies).

Software Engineer. The software engineer will be responsible for programming and managing the OARSCM mobile application and ensuring all data is flowing correctly between the mobile application and the secure server. They will have access to identified data within the Q2i OARSCM secure server at AWS. This data will include the patient's name (first and last), DOB, email address, cell phone number, urine toxicology results, and attendance in treatment. PHI will be directly entered into the mobile application. Q2i will have access to the server via secure shell terminal sessions. The OARSCM mobile application does not store PII/PHI locally on the device.

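### SBIRT, shared by both arms, is assigned to different providers in different sections, and section 24 has it given by a research assistant who already knows the allocation

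*Protocol*

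**What the plan says.** Protocol section 24 (Phase 2 Aims 1 & 2) sets out the enrolment visit: "After the RA consents the participant, they will open a randomization envelope and randomize the patient to either TAU or OARSCM". It continues: "For TAU the participant will receive SBIRT provided by the RA, a warm handoff to a community MOUD treatment facility", with training on MyMAT. OARS+CM participants are then said to get this same usual care, with the study app in place of MyMAT.

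Other sections describe the same component differently:

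- Section 5 (Procedures, TAU with MyMAT) says of the hospital's Behavioral Health Service that it "provides SBIRT for substance use disorders, including OUD. They provide SBIRT as part of TAU", with a handoff to outpatient treatment where possible.
- Section 6 (Interventions, Group A) describes usual care as including "brief counseling and referral to treatment by a social worker or other behavioral health provider". The term SBIRT is not used there, but the content is the same.
- Section 23 gives research assistants the screening log and "enrolling participants conducting interviews and completing telephone outcome assessment services". SBIRT is not on the list.
- The Phase 2 table in section 11 has one onboarding row: "App training, warm hand-off scheduling outpatient Suboxone intake".

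The SAP (Phase 2, RCT) names two primary outcomes: the proportion who schedule an intake visit and the proportion who complete it.

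**The concern.** Counselling, referral and handoff exist to get a patient to an intake appointment, so they act directly on both primary outcomes. They are also meant to be constant across arms, so that a difference can be credited to OARS+CM.

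If a research assistant counsels the patient after seeing the allocation, effort can vary with the arm without anyone intending it. More persistence in the OARS+CM arm would inflate the apparent effect. Extra effort for controls, to make up for the missing prizes, would shrink it. Section 5 adds a reason for the contact to feel different: only OARS+CM patients earn a guaranteed $5 prize for scheduling the intake and a $20 prize for completing it.

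A second issue is what the control represents. Counselling by study staff is not the usual care that sections 5 and 6 describe.

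**Working it through.** The plan states no figure on this point, so the check compares the sections.

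**1. Who delivers it, and when**

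| Protocol section | Provider of counselling/SBIRT | Timing against allocation |
|---|---|---|
| 5, Procedures | Behavioral Health Service | Not stated |
| 6, Group A | Social worker or other behavioral health staff | Not stated |
| 23, Research Assistant(s) | SBIRT absent from the duties | Not applicable |
| 24, Phase 2 | Research assistant | Listed after the envelope is opened |

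Sections 5 and 6 are compatible with each other. Section 24 agrees with neither, and section 23 does not support it. Research assistant SBIRT could be an addition to the clinical service's own, but no section says so.

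**2. Is a difference between arms planned?** No. Sections 5, 6 and 24 each say that OARS+CM participants receive the same usual care as controls. Section 24 therefore carries its research assistant SBIRT into both arms.

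**3. Does the provider mismatch by itself create a difference?** No. Any single provider used equally in both arms would leave the arms balanced. The exposure comes from combining two things in section 24: delivery by study staff, and delivery after the allocation is known.

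**4. Does the component reach the primary outcomes?** Yes. Under sections 5 and 6 the handoff can include a scheduled appointment, and scheduling is itself a primary outcome. The section 11 table puts app training and handoff scheduling in one step. App training depends on the arm, so that step follows allocation.

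**5. Does the analysis correct for it?** No. Intention-to-treat analysis does not remove unequal co-intervention after randomisation. The covariates listed in the SAP are participant characteristics and service use. None records who gave SBIRT or when.

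**6. Can a size be given?** No. The documents contain no estimate of unequal delivery. Even an assumed shift has no stable meaning, because the SAP's 50% increase from 35% can be read in two ways:

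- relative: 0.35 × 1.5 = 0.525, a difference of 17.5 points;
- absolute: 0.35 + 0.50 = 0.85, a difference of 50 points.

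A purely hypothetical 5-point shift (0.05 × 51 = 2.6 intakes per arm) would be 5/17.5 = 29% of the first difference and 5/50 = 10% of the second. A 10-point shift (0.10 × 51 = 5.1 intakes) would be 57% or 20%. The spread shows why no figure should be attached; it is not an estimate.

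**The case against.** The strongest reply is that this is a drafting inconsistency. The same usual care is promised in both arms in three places, and unequal delivery is a conjecture about staff behaviour. That stands as far as it goes: a reader might infer that the arms will receive different amounts of counselling, and the documents do not support that.

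Four further objections also hold in part.

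- **Contact before allocation.** The eligibility criteria in section 6 exclude patients who decline referral to the listed clinics or do not want MOUD treatment, and they require a clinical judgement of suitability. Some referral discussion therefore precedes randomisation. This narrows the room for bias, but it does not say when SBIRT takes place.
- **Who does what.** Section 24 names no Phase 2 app trainer and nobody to perform the handoff. It is tempting to say that one research assistant counsels, trains and books the intake. That is plausible but not documented; the research assistant is named as app trainer only for Phase 1.
- **The unseen grant.** Section 14 on fidelity and section 24 on procedures both defer to the grant. A script or fidelity check may be there, so one cannot claim that the trial has none.
- **The comparison with usual care.** A reader might conclude that research assistant SBIRT invalidates the comparison. It does not. If given in both arms, the randomised contrast stands, and what changes is how well the control represents local usual care.

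None of this answers the remaining point: as section 24 is written, someone who knows the arm delivers a shared component that bears on the primary outcomes.

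**Conclusion.** The point holds as an inconsistency between sections with an avoidable risk of performance bias in either direction. It is not evidence of an imbalance, planned or actual. It rests on reading the order of steps in section 24 as their order in time, and on the supplied text alone. The size of any bias cannot be calculated from the documents. This is a cheap improvement to the design rather than a fault that undermines the trial.

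**What to change.** 1. Reconcile sections 5, 6, 23 and 24 on who delivers SBIRT and who performs the handoff. Which provider is right is for the sponsor to decide.
2. Where study staff deliver SBIRT, complete it before the envelope is opened. Section 6 says that assignment uses REDCap; if so, complete it before the assignment is displayed.
3. Record in REDCap, for each participant, who delivered SBIRT and whether it preceded allocation, so that delivery can be compared by arm.

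The cost is a small change in visit order, the clarifying text and two data fields. The fix is partial: intake scheduling and app training still follow allocation and stay unblinded, and scheduling is itself a primary outcome. If the grant already contains a script or fidelity check, the Protocol should cite it at this step.
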